## 9 Adverse Events

#### 9.1 Adverse Events Definitions

In this study, an Adverse Event (AE) is any undesirable clinical occurrence (sign, symptom, illness, or other medical event), that appears or worsens during the clinical study, or requires medical treatment or intervention to a subject, whether it is considered to be device-related or not. If an adverse event occurs, the first concern will be the safety and welfare of the patient. Appropriate medical intervention will be made.

Any AE or complication reported by the patient or observed by the physician that occurs during or after treatment with the device will be recorded in the medical record or source document and on the Case Report Form (CRF). The investigator will determine if the AEs are device-related or procedure-related. This assessment shall include the onset date, resolution date, severity, seriousness, frequency, treatment and outcome.

Each AE should be assessed according to the following criteria:

### 9.1.1 Severity

Each AE should be assessed for its severity, or the intensity of an event experienced by the subject.

Mild: Awareness of a sign or symptom that does not interfere with the subject's activity or is transient

Confidential 15

resolved without treatment and has no sequelae.

**Moderate:** May interfere with the subject's usual activity and require additional intervention and/or treatment, and may have additional sequelae.

**Severe:** Significant discomfort to the subject and/or interferes with the subject's activity. Additional intervention and or treatment are necessary. Additional sequelae occur. Severe is used to describe the intensity of an event experienced by the subject.

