Main Skin Related Exclusion Criteria  Investigational Treatment and	
 
Pregnant or intending to become pregnant during the course of study. A urine pregnancy test will be given to women of childbearing potential and performed during initial visit.
 
Having any active electrical implant anywhere in the body, such as a pacemaker or an internal defibrillator.
 
Having a permanent implant in the treated area.
 
Each subject will receive three treatments at four week intervals and return for follow-up visit at one (± seven days) month after the last
 

Study Duration	treatment for evaluation of the treated areas.
Criteria for Evaluation	
 
Number and type of any adverse events throughout the study will be recorded.
 
General skin appearance improvement at FU3 compared to baseline as assessed by independent evaluators by photographic assessment, utilizing the GAI Scale.
 
Secondary endpoints
 
Subject's assessment of pain associated with treatments using a VAS scale, following each of the 3 treatments.
 
Investigator assessment of immediate and short term response following each treatment, defined as type and intensity of response and the time it takes for it to subside.
 
Subject's satisfaction with the results and assessment of improvement in skin appearance using a GAI scale.
 
Subject's vaginal pH with results from pH paper sampling of the vaginal mucosa.
 
Subject's histologic and molecular pathology changes with standard
 

Confidential 3

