#### 8.3 Study Analysis

• An intermediate safety report based on qualitative analysis of immediate and short term reaction and on AEs will be produced based on analysis of data collected immediately post treatment number one of all the enrolled subjects. This data will be used to adjust further treatments parameter. The interim

Confidential 14

- reports will not affect the continuation of the study. The study will, regardless of the interim report results, be finalized according to this protocol.
- After FU3, the photographs will be sent to independent evaluators that will grade on a GAI scale the change in skin laxity according to photograph of FU3 compare to baseline. Descriptive statistics and correlations between variables will be performed on these results.
- After FU3 the subject assessment on the change in skin laxity on a GAI scale will be analyzed. These results will be correlated with the evaluation done by the independent evaluators in order to learn on the relationships between objective and subjective improvements assessments.
- After FU3 all data collected by response and discomfort/pain level (VAS) and the 5-level short term response scale results will be analyzed using descriptive statistics.
- After FU3, the vaginal pH values will be sent to the PI for formal data entry and analysis. These results will be correlated with the evaluation done by the independent evaluators in order to learn on the relationships between objective and subjective improvements assessments.
- After FU3, the histology slides and molecular assay results will be sent to the PI for formal data entry
  and analysis and archive storage (histology slides). These results will be correlated with the evaluation
  done by the independent evaluators in order to learn on the relationships between objective and
  subjective improvements assessments.

The study reports will provide information for use in research & development, and future planned studies. Descriptive statistics and correlations between variables will be performed.

Safety: Adverse events reported will be listed, documenting course, outcome, severity, and possible relationship to the treatment.

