## 9.1.5 Diagnosis of Adverse Event

There should be an attempt to report a "diagnosis" rather than the individual signs, symptoms and abnormal laboratory values associated with the diagnosis. However, a diagnosis should be reported only if, in the Investigator's judgment, it is relatively certain (i.e., definite or possible). Otherwise individual signs, symptoms and abnormal laboratory values should be reported as the adverse events.

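### The adverse event severity grades in Section 9.1.1 are not mutually exclusive: read plainly, every event that meets Severe also meets Moderate, and Severe requires sequelae

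*Combined protocol and SAP*

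**What the plan says.** Section 9.1.1 opens by equating severity with intensity: "Each AE should be assessed for its severity, or the intensity of an event experienced by the subject". It then defines three grades, given here from the highest down.

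- Severe is worded as "Significant discomfort to the subject and/or interferes with the subject's activity. Additional intervention and or treatment are necessary. Additional sequelae occur". A closing sentence repeats that the term describes intensity.
- Moderate is worded as "May interfere with the subject's usual activity and require additional intervention and/or treatment, and may have additional sequelae". Interference and sequelae are thus optional.
- Mild is worded as "Awareness of a sign or symptom that does not interfere with the subject's activity or is transient", continued after a page break as "resolved without treatment and has no sequelae".

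The section does not say what to record when an event meets two grades or none. In the analysis, Section 8.3 uses the grade in one place: "Adverse events reported will be listed, documenting course, outcome, severity, and possible relationship to the treatment". The synopsis criterion for safety is "Number and type of any adverse events throughout the study will be recorded", which does not mention severity.

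**The concern.** A severity scale should give each event one grade. Here intensity, treatment, duration and sequelae are mixed, and the grades do not step up on any one of them. Moderate is worded so permissively that it appears to contain Severe. Severe carries a sequelae condition that has nothing to do with how intense the event was.

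Safety of both applicators heads the primary objectives (Section 3.1). No safety test or threshold is planned, so the adverse event (AE) safety result is essentially the Section 8.3 listing, and severity is one of the four attributes it names. Appendix I has the IRB review safety in the first 10 patients before an expansion to as many as 300. In a listing from 10 patients, one event graded differently is visible.

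**Working it through.** The documents give no figure to reproduce. The check is logical: list every combination of the attributes that Section 9.1.1 uses and count the grades each one meets.

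**Attributes (yes/no).** I = interferes with activity; D = significant discomfort; T = treatment needed; S = sequelae; R = transient. This gives 2^5 = 32 profiles. They are logical cases, not expected events, and they are not equally likely.

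**Readings of the text.**

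- Severe, plain reading: its three sentences apply together, so (D or I) and T and S.
- Moderate, strict: T is needed, with I and S optional. Moderate, loose: *may* also governs *require*, so nothing is needed.
- Mild A: the closing clause limits only transient events, so not-I, or (R, not-T and not-S).
- Mild B: the closing clause limits the whole definition, so (not-I or R) and not-T and not-S.
- Mild C: no sequelae applies throughout, no treatment only to transient events, so (not-I, or R and not-T) and not-S.

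**Step 1, overlap.** Severe profiles: 3 combinations with D or I, T and S fixed, R free, so 3 × 2 = 6. All have T = 1, so all 6 meet strict Moderate, and they meet loose Moderate trivially. The result is 6 of 6 under every reading of Mild and Moderate.

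**Step 2, sequelae.** A profile with D = 1, I = 1, T = 1 and S = 0 fails Severe however intense the event was. At the other end, a transient, untreated event without sequelae that interferes with activity meets Mild under A, B and C, whatever the discomfort. With strict Moderate, Mild is its only grade.

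**Step 3, gap under strict Moderate.** An interfering event is ungraded if T = 0 and it is not both transient and free of sequelae. With D free, this is 2 × 3 = 6 profiles under each reading of Mild.

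**Step 4, all profiles, Severe read jointly.** Moderate holds 16 profiles (strict) or 32 (loose).

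| Mild reading | Profiles in Mild | Strict: no grade | Strict: more than one | Loose: no grade | Loose: more than one |
|---|---|---|---|---|---|
| A | 18 | 32 − (18 + 16 − 8) = 6 | 8 + 6 − 2 = 12 | 0 | 18 + 6 − 2 = 22 |
| B | 6 | 32 − (6 + 16) = 10 | 6 | 0 | 6 + 6 = 12 |
| C | 10 | 32 − (10 + 16 − 4) = 10 | 4 + 6 = 10 | 0 | 10 + 6 = 16 |

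Under strict Moderate, the Mild-and-Moderate overlap is 8 profiles in A, none in B and 4 in C. In A, 2 profiles meet all three grades. The 4 extra ungraded profiles in B and C do not interfere with activity; they are untreated events with sequelae.

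**Step 5, other readings of Severe.** If any one criterion is enough, Severe holds 30 profiles, of which 16 also meet strict Moderate. If only discomfort or interference counts, it holds 24, of which 12 do. No interfering profile is then ungraded. Across all 3 × 2 × 3 = 18 readings, none gives every profile exactly one grade.

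**The case against.** The best defence is that the text can be read more kindly. Severe is three separate sentences with no *and* between them, and its closing sentence points back to intensity. If one criterion is enough, Severe is only partly contained in Moderate (16 of 30), and a painful event that heals can be Severe. Likewise, *may* can govern *require*, and then no event is ungraded. Both readings are possible, so the gap and the full containment are conditional. What does not go away is that no reading tried makes the grades exclusive, and no tie rule is written.

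The defence is also right about the reach of the problem. A reader might infer that the whole severity column is undetermined, but some profiles are clear: a transient, non-interfering, untreated event with no sequelae and no significant discomfort is Mild only, with strict Moderate and Severe read jointly. A reader might infer a downward bias, but the overlap permits the lower grade without compelling it, and nothing shows how raters would choose.

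A reader might also take the heading of Section 9.2.1, which expands SAE as severe, to mean that the grade triggers reporting. The text beneath it and Section 11 say serious, Section 9.1.3 separates the two terms, and Appendix I reports burns of any degree under its own procedure.

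Finally, Section 9.1.5 treats a possible diagnosis as relatively certain, and a reader might infer that observed signs could drop out of the listing. That is a separate matter and largely covered: Section 9.1.6 requires anticipated events to be recorded, and Appendix G asks about crusting and blistering by name.

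**Conclusion.** The point holds as a defect in the grading rule. With the Severe conditions read jointly, which is the plain reading, 6 of 6 Severe profiles also meet Moderate, and Severe cannot be assigned without sequelae even though the section defines severity as intensity. If Moderate also requires treatment, 6 interfering profiles of 32 have no grade (6 to 10 ungraded in all), and 6 to 12 have more than one. If it does not, none is ungraded, but Moderate admits all 32 and separates nothing.

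The consequence is that some severity entries in a descriptive listing depend on the rater, with room for under-grading. How many real events this would affect cannot be derived from the documents. The count and type of events, and the reporting of serious events, do not use the grade. This is a modest weakness, worth correcting because it sits under a primary safety objective and costs almost nothing to remove.

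**What to change.** Rewrite the three grades in Section 9.1.1 on intensity alone:

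- Mild: no interference with usual activity.
- Moderate: some interference.
- Severe: prevents usual activity or causes significant discomfort.
- If two grades apply, record the higher.

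Take treatment and sequelae out of the grades and keep them in the treatment and outcome fields that Section 9.1 already collects.

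Checked the same way, three levels of interference by discomfort yes/no give 6 profiles. All are graded, and 2 meet two grades (significant discomfort with no interference, or with some). The higher-grade rule settles both, so each profile has exactly one grade.

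A tie rule alone would settle the overlap, but it would leave the sequelae condition in Severe and, under strict Moderate, the gap. The cost is one paragraph of protocol text and matching labels on the case report form. No new data are needed.

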## 9.1.2 Relationship of AE to the Device

Each AE should be assessed for its relationship to the device or procedure as identified as follows:

**Device:** This category should be restricted to adverse events directly attributable to the modified Venus Concept Versa

Procedure: A procedure is any activity that supports the usage of the device

Use the following categories for assigning the certainty of the relatedness:

**Related** – The AE is known to occur with the study agent, there is a reasonable possibility that the study agent caused the AE, or there is a temporal relationship between the study agent and event. Reasonable possibility means that there is evidence to suggest a causal relationship between the study agent and the AE.

**Not Related** – There is not a reasonable possibility that the administration of the study agent caused the event, there is no temporal relationship between the study agent and event onset, or an alternate etiology has been established.

#### 9.1.3 Serious Adverse Events

NOTE: The term serious is not synonymous with severity, which may be used to describe the intensity of an event experienced by the subject). An AE that does not meet any of the below criteria will be classified as non-serious.

A serious AE is any event that:

- Results in, or contributes to a death;
- Is immediately life-threatening (injury or illness);
- Results in hospitalization, or prolongs an existing hospitalization;
- Results in permanent impairment of body structure or function, or in persistent or significant disability/incapacity;
- Results in an injury that requires medical intervention to prevent permanent impairment of body structure or function;
- Is a device malfunction or deterioration in the characteristics and/or performance of the device that results in death or serious deterioration in health;
- Is a device malfunction or deterioration in the characteristics and/or performance of the device that, if it were to occur again, could result in death or serious deterioration in health;
- Results in a congenital anomaly or birth defect.
- Is any medically significant injury, event or experience that requires medical/surgical intervention to

Confidential 16

prevent one of the outcomes listed above;

• Results in end- organ toxicity, including hematological, renal, cardiovascular, hepatic, gastrointestinal, and central nervous system events;

### 9.1.4 Pre-existing Conditions

A pre-existing condition should not be reported as an adverse event unless there has been a substantial increase in severity or frequency of problems, which has not been attributed to natural history.

## 9.1.5 Diagnosis of Adverse Event

There should be an attempt to report a "diagnosis" rather than the individual signs, symptoms and abnormal laboratory values associated with the diagnosis. However, a diagnosis should be reported only if, in the Investigator's judgment, it is relatively certain (i.e., definite or possible). Otherwise individual signs, symptoms and abnormal laboratory values should be reported as the adverse events.

#### 9.1.6 Anticipated Outcome Related Adverse Events

Anticipated adverse events in this study include pain, tenderness, purpura, persistent erythema, edema, burn, blistering, crusting, hyperpigmentation, hypopigmentation, scarring and potential for damage to hair follicles within the treatment area and subsequent loss of hair within the treatment area.

Any anticipated AE that occurs at any time during or after the use of the study device must be recorded by the Investigator. If the anticipated AE, in the opinion of the Investigator, is likely to affect the safety of the subjects or the conduct of the study, the ethic committee will be notified of the effect within 10 working days. In this study if an adverse event occurs the Investigator will continue following the subject until the case is resolved or up to 1 month following the last visit, whichever comes first.

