## **Study Synopsis**

	· · · ·				
Study Title	Clinical evaluation of the safety and Efficacy of using Multi-Polar RF and PEMF technologies for the treatment of the Mons Pubis, Vaginal Introitus and Labia Skin Laxity				
Protocol No:	CS2815				
Device Name:	Modified Venus Versa (MP)  device with Freeze Diamondpolar and Investigational Applicators				
Design	Feasibility, single-center, baseline-controlled, prospective study				
Projected Study period	Initiation Date: February 2016 Completion Date: February 2017				
Objectives	
 
Primary objectives
 
To evaluate the safety of treating the mons pubis, labia and vaginal introitus with the Freeze Diamond Polar applicator.
 
To evaluate the safety of the internal treatment of the vagina with an investigational applicator
 
To verify the efficacy of using the Freeze Diamond Polar applicator for improving general skin appearance of the mons pubis, vaginal introitus and the labia including improvement of skin irregularities and skin laxity.
 
To determine and/or quantify any potential regenerative properties associated with the study treatments.
 
Secondary objectives
 
To evaluate subject's assessment of comfort and pain associated with treatments.
 
To evaluate subject's satisfaction with treatment results and assessment of improvement.
 
To determine if any regenerative properties are associated with the
 
				
Hypothesis	
 
Mons pubis, Vaginal Introitus and the Labia.
 
The study will confirm that the Freeze Diamondpolar applicator is safe for treating the mons pubis, labia and vaginal introitus which will result in improvement in general skin appearance including an improvement in skin irregularities and skin laxity.
 
The study will confirm that the investigational applicator is safe for
 
				
Study population	internal treatment of the vagina.  1 site with 10 subjects				
Main Inclusion Criteria	
 
Healthy female between the ages of 25 and 65.
 
Sexual activity (vaginal intercourse once per month) in a monogamous relationship.
 
Requesting aesthetic benefit to the vaginal mons, introitus and labia.
 
				

Confidential 2

Protocol: CS2815v4 Approval Number: IRCM-

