#### SAFETY SOP FOR POTENTIAL BURNS:

The following SOP shall be conformed to at all study facilities if a patient experienced any first, second or third degree burn or pain beyond narcotics:

- 1. The event will be reported to the study Director within 24 hours of occurrence.
- 2. A copy of the patient chart and treatment parameters are to be forwarded to the study Director within 24 hours.
- 3. Immediate triage and treatment of the patient shall be determined by the treating physician and based upon severity and type of burn identified.
- 4. The study Director will be responsible for issuing a written report to the company and the IRB Chairman no later than 7 days from the incident.
- 5. Long term follow up and care shall continue at the discretion of the treating physician.
- 6. All patients experiencing a complication of the device will be followed a minimum of 2 years following the initial injury. Longer care and observation will be at the discretion of the treating physician.
- 7. All minor complications such as appearance or altered sensation, except for pain, can be reported within 30 days of patient complaint. Both chart and treatment parameters are to be provided to the study Director and shared with the company and IRB chairman.

Confidential 30

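### For a burn, section 9.1.6 caps follow-up at 1 month after the last visit while the Appendix I burn SOP requires at least 2 years, and nothing says which rule prevails

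*Combined protocol and SAP*

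**What the plan says.** Section 9.1.6 defines the anticipated events: "Anticipated adverse events in this study include pain, tenderness, purpura, persistent erythema, edema, burn, blistering, crusting, hyperpigmentation, hypopigmentation, scarring", among others. For an adverse event in this study, it then says that "the Investigator will continue following the subject until the case is resolved or up to 1 month following the last visit, whichever comes first". It also sets a conditional notice rule. If an anticipated event, "in the opinion of the Investigator, is likely to affect the safety of the subjects or the conduct of the study", then "the ethic committee will be notified of the effect within 10 working days".

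Appendix I contains a separate safety SOP for potential burns. It "shall be conformed to at all study facilities if a patient experienced any first, second or third degree burn or pain beyond narcotics". Item 4 makes the study Director responsible for "issuing a written report to the company and the IRB Chairman no later than 7 days from the incident". Item 5 leaves long-term care to the treating physician. Item 6 says: "All patients experiencing a complication of the device will be followed a minimum of 2 years following the initial injury". Only observation beyond that period is left to the physician's discretion.

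Section 9.1.6 neither mentions the SOP nor makes an exception for burns. Section 9.3.1 does refer to Appendix I, but only for safety background.

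**The concern.** A burn falls under both texts: 9.1.6 names it, and it triggers the SOP. An investigator who applies 9.1.6 as written closes the case when the burn resolves or 1 month after the last visit, whichever is sooner. An investigator who applies the SOP keeps the subject under follow-up for at least 2 years.

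The safety of both applicators is a primary objective (section 3.1), and section 8.3 says adverse events will be listed with their course and outcome. What that listing shows for a burn, and how long the injured subject is observed, therefore depends on which rule is applied.

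**Working it through.** **Inputs from the documents**
- Treatments are four weeks apart (sections 2 and 7.1, Appendix A): days 0, 28 and 56.
- The last visit is Visit 4 (FU3), placed 4 weeks after treatment 3 in Appendix A: day 56 + 28 = 84. Section 7.1 gives it as one month, ± seven days.
- 9.1.6 ceiling: resolution, or 1 month after the last visit if sooner.
- SOP item 6 floor: 2 years after the initial injury.

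**Assumptions**
- The last visit means FU3.
- The month after the last visit is 30 days, and 2 years is 2 × 365 = 730 days.

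**Longest follow-up under 9.1.6.** The latest stopping day is 84 + 30 = 114. Follow-up after injury = 114 − day of treatment.
- Burn at treatment 1: 114 − 0 = 114 days; 114/730 = 15.6%; shortfall 730 − 114 = 616 days.
- Burn at treatment 2: 114 − 28 = 86 days; 86/730 = 11.8%; shortfall 730 − 86 = 644 days.
- Burn at treatment 3: 114 − 56 = 58 days; 58/730 = 7.9%; shortfall 730 − 58 = 672 days.

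These are maxima. A burn that heals sooner is released sooner under 9.1.6, but not under item 6.

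**Sensitivity.** Take FU3 as 28 or 30 days after treatment 3, with ± 7 days.
- Shortest (treatment 3): 28 − 7 + 30 = 51 days; 51/730 = 7.0%.
- Longest (treatment 1): 56 + 30 + 7 + 30 = 123 days; 123/730 = 16.8%.

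No reading of the visit window or the month brings the ceiling near the floor.

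**Study calendar.** The synopsis gives "Completion Date: February 2017", with initiation in February 2016. A burn in February 2016 would need follow-up to February 2018, 12 months after the stated completion. Section 7.1 expects completion within six months, and Appendix A has no visit after Visit 4.

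**IRB notice, side by side**
- 9.1.6: within 10 working days, only if the Investigator judges that safety or conduct is likely to be affected. Ten working days are 12 to 14 calendar days, depending on the starting weekday and ignoring public holidays.
- SOP item 4: written report within 7 days of the incident, for every burn, by the study Director.

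A report within 7 days also meets a limit of 12 to 14 days, and neither rule forbids the other. There is no contradiction here. What is missing is a pointer from 9.1.6 to the stricter duty.

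**The case against.** **The specific rule governs the general one.** Section 9.1.6 is a general adverse-event paragraph; the SOP is headed for burns, has its own trigger and is mandatory. A careful site would probably apply the stricter rule. That is a sensible inference, but the protocol does not state it, and the one pointer from the adverse-event section describes Appendix I as background. The argument lowers the chance of a wrong choice without removing the contradiction.

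**The 2 years may be clinical care after the study.** Item 5 and the end of item 6 speak of care at the treating physician's discretion. But the 2-year minimum itself is worded as an obligation, in an SOP that facilities must follow, and discretion begins only after it. This reading is possible but not stated.

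**The timetable does not settle it.** A reader might infer from Appendix A and the completion date that the short rule was intended. Those texts describe scheduled visits for all subjects; event-driven follow-up of an injured subject would not normally appear there. The dates show only that no provision is made for the longer period.

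**Item 7 does not help.** It allows 30 days to report minor complications. It does not shorten item 6 for burns.

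**The practical impact may be small.** Section 9.3.1 lists burn among low-probability effects, and Appendix I says thermal control makes burns very unlikely. The conflict matters only if a burn occurs. The photographic primary endpoint is unaffected. This stands.

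**A stronger reading on IRB notice.** A reader might infer that the 7-day and 10-working-day rules also contradict each other. They do not: the SOP adds a stricter layer, and a site bound by it cannot rely on 9.1.6 alone.

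**Conclusion.** Wrong as written: an internal contradiction in a safety rule. For a burn, 9.1.6 ends follow-up at no more than about 114, 86 or 58 days after injury at treatment 1, 2 or 3 (51 to 123 days over the range examined), while SOP item 6 requires at least 730. The ceiling is about 8% to 16% of the floor (7% to 17% over the range), and no text gives either rule precedence. This rests on taking the last visit as FU3 and on item 6 as an obligation of the study, which is how it is worded. No burn rate is assumed.

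A reader might go further and conclude that every device-related adverse event is caught in the same contradiction. Item 6 is worded widely enough to suggest it, but the SOP opens with a narrower trigger (any burn, or pain beyond narcotics), and the documents do not settle which scope is meant. The contradiction is established for burns; for device-related blistering, scarring or pigment change it depends on that unresolved scope. Nor do the documents show that late harm would be missed, since they do not say when such effects would appear.

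**What to change.** 1. In 9.1.6, exempt events covered by the Appendix I SOP from the limit of resolution or 1 month after the last visit. State that they are followed for at least 2 years after the injury, and cross-refer to Appendix I for the written IRB report within 7 days.
2. In SOP item 6, state whether it covers only the SOP's triggers (any burn, or pain beyond narcotics) or every device-related complication. Make the 9.1.6 exemption match, and keep the 1-month limit only for events outside that scope. If the scope is left open, the same contradiction could remain for blistering, scarring and pigment change.
3. State that cases still in follow-up at study completion are reported as ongoing, with a later addendum. A note to Appendix A can provide for the extra contacts for affected subjects only.
4. If 2 years is not intended, correct item 6 instead, with IRB agreement.

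The cost is a few sentences and cross-references; endpoints and sample size do not change. The downside is that an affected subject must be tracked beyond the planned study end, and her final outcome would come after the main report. Under its own wording, the SOP already commits the study to that follow-up.
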